**Commercially Confidential Information** 

However, efficacy of the inhaled therapies (such as LABA/LAMA, LABA/ICS, LABA/LAMA/ICS) is not expected to be impacted due to the delivery directly to the lungs. In addition to the inhaled therapies, as a perpetrator, QBW251 is not expected to have impact on the PK exposure of the macrolides (such as Erythromycin and Clarithromycin) as they are no substrates of metabolite enzymes of CYP1A2, 3A4 or UGTs.

Please refer to the respective labels of the background therapy for additional information on drug interactions. Any concomitant medications should be noted in the eCRF. As additional information becomes available when clinical drug interaction studies are conducted during the QBW251 development program, this information will be further updated and reflected in the QBW251 Investigator Brochure.

### Benefits

With respect to clinical benefits, a proof of concept study showed a statistically significant and clinically relevant decrease in systemic inflammation (fibrinogen; based on expert opinion), an improvement of pulmonary function (FEV1) and a reduction of the bacterial load of selected pathogens after 4 weeks of treatment with QBW251 in COPD subjects.

Finally, an independent Data Monitoring Committee will oversee the developing clinical database to support ensuring subjects' well-being throughout the study.

#### 4.5.1 Blood sample volume

A volume smaller than a typical blood donation (approximatively 150 mL) is planned to be collected during Screening, Baseline, during the 12 weeks of the treatment period and at the end of the study, from each subject. For subset of subjects participating to serial PK sampling, approximatively 30 mL will be collected in addition.

Additional samples may be required for safety monitoring.

Timings of blood sample collection are outlined in the assessment schedule (Table 8-1).

A summary blood log is provided in the Site Operations Manual (SOM). Instructions for all sample collection, processing, storage and shipment information is also available in the SOM and Central laboratory manual.

See Section 8.5.3.1 on the potential use of residual samples.

#### 5 **Population**

The study population will consist of approximately 100 male and female subjects, aged 40 years old and above, with moderate to severe COPD (GOLD 2 to 3) with features of chronic bronchitis, a smoking history of at least 10 pack / years, and at least two moderate or one severe exacerbation(s)between January 2019 and their screening visit. All subjects must have a plasma fibringen level of ≥ 320 mg/dL, a CAT score of at least 10, and have been on LAMA/LABA or LABA/ICS or LABA/LAMA/ICS therapy at stable dose for at least 3 months prior study start. COPD subjects are allowed to stay on macrolides as background therapy if they have bronchiectasis as a secondary diagnosis and if they have been treated with them for at least 3 months at stable dose before study start. In addition, subjects' sputum must be colonized with potentially pathogenic bacteria (>0 CFU) at screening.

#### 5.1 Inclusion criteria

Subjects eligible for inclusion in this study must meet all of the following criteria:

- 1. Patients who have signed an Informed Consent Form prior to initiation of any study-related procedure.
- 2. Male and female adults aged ≥40 years at screening.
- 3. Patients with stable COPD, stages GOLD 2-3, according to the current GOLD strategy (GOLD 2019) at screening.
  - Patients with a post-bronchodilator FEV1/FVC < 0.70 at screening
- 4. Superseded as of amendment V01
  - 4a. Patients with airflow limitation indicated by a post-bronchodilator FEV1 > 30% and FEV1 < 80% of the predicted normal at Screening who must have had at least 2 documented moderate or at least 1 documented severe exacerbation(s) between January 2019 to study screening

Notes:

- Post-bronchodilator refers to 15 to 30 min after inhalation of 400 μg salbutamol/360 µg albuterol (or equivalent dose).
- Exacerbations are defined as moderate if leading to treatment with systemic glucocorticosteroids and/or antibiotics, and as severe if leading to hospital admission or emergency room visit lasting > 24 h in addition to treatment with systemic glucocorticosteroids and/or antibiotics.
- Patients not meeting the FEV1 criteria may be re-screened once.
- 5. 5 and 5a: Superseded as of amendment V02
  - 5b. Patients with sputum positive (>0 CFU) for at least one strain of potentially pathogenic microorganism at screening (H influenzae, H parainfluenzae, P aeruginosa, S pneumoniae, S aureus, Moraxella catarrhalis, Enterobacteriaceae, Stenotrophomonas maltophilia, Burkholderia species, and Achromobacter species or any potential pathogenic bacteria measured by dilution/outgrowth. Any organism that is to be included and that is not included in the list of the protocol defined pathogens will be discussed case by case). Sputum samples may be re-collected and re-tested once during the screening period.
- 6. Patients who have been treated with a combination of LABA/LAMA or LABA/ICS or LABA/LAMA/ICS at a stable dose for the last 3 months prior to screening. COPD patients are allowed to stay on macrolides as background therapy if they have bronchiectasis as a secondary diagnosis and if they are treated with them at a stable dose 3 months before screening.

Note: Fixed or free combinations are acceptable.

- 7. Superseded as of amendment V01
  - 7a. Patients with plasma fibrinogen level  $\geq$  320 mg/dL at screening. Fibrinogen may be re-tested once during the screening period.
- 8. A COPD Assessment Test (CAT) score of at least 10 at screening.
- 9. Current or ex-smokers who have a smoking history of at least 10 pack years (e.g. 10 pack years = 1 pack/day x 10 years, or 0.5 pack/day x 20 years) at screening.
  - Note: A pack of cigarettes is equal to 20 cigarettes. Bidi or other similar non-filtered cigarette may be considered applicable to smoking history. They should be counted in the same way as standard cigarettes. Occasional smoking of cigars, pipes, e-cigarettes, or inhaled nicotine products are not relevant to smoking history.
  - Note: An ex-smoker is defined as a subject who has not smoked for≥ 6 months at screening or at the time of assessment.
- 10. Patients featuring chronic bronchitis, defined as productive cough that occurs on most days (defined as >50% of days) during at least 3 consecutive months in the year prior to screening, as assessed by documentation of patient recollection (anamnesis) or documented in patients' records.
- 11. Able to communicate well with the investigator, to understand and comply with the requirements of the study.

#### 5.2 **Exclusion criteria**

Subjects meeting any of the following criteria are not eligible for inclusion in this study.

- 1. Patients with a history of long-OT syndrome or whose OTcF interval at screening (Fridericia method) is prolonged (QTcF > 450 ms in males, > 460 ms in females).
- 2. Superseded as of amendment V01 2a. Patients who have a clinically significant\* ECG abnormality before randomization. Note: Clinically significant abnormalities may include but are not limited to the following:

left bundle branch block, Wolff-Parkinson-White syndrome, clinically significant arrhythmias (e.g., atrial fibrillation, ventricular tachycardia).

- 3. Clinical laboratory values abnormalities (including Gamma GT, AST, ALT, total bilirubin or creatinine) considered as clinically significant\* in the opinion of the Investigator at screening. For additional guidance on hepatic parameters see exclusion criterion #5.
- 4. Patients who have clinically significant\* renal, cardiovascular (such as but not limited to unstable ischemic heart disease, NYHA Class III/IV left ventricular failure, myocardial infarction), neurological, endocrine, immunological, psychiatric, gastrointestinal, or hematological abnormalities, which could interfere with the assessment of the efficacy and safety of the study treatment, or patients with uncontrolled Type II diabetes.
  - \* Note: Clinically significant is defined as any disease that, in the opinion of the investigator, would put the safety of the patient at risk through participating, or which would affect the efficacy or safety analysis if the disease/condition exacerbated during the study, or would compromise patient compliance or preclude completion of the study.
- 5. Superseded as of amendment V01
  - 5a. Patients with a history or current treatment for hepatic disease including but not limited to acute hepatitis, cirrhosis or hepatic failure.
  - Patients with stable chronic hepatitis may be included in the study by agreement with Novartis Medical Expert on a case-by-case basis.
  - A history of resolved Hepatitis A is not exclusionary.
  - Patients with prothrombin time international normalized ratio (PT/INR) of more than 1.5xULN at screening. Patients excluded for the PT/INR of more than 1.5xULN can be re-screened when the values have returned to normal.
- 6. Patients with a history of malignancy of any organ system, treated or untreated, within the past 5 years whether or not there is evidence of local recurrence or metastases, with the exception of localized basal cell carcinoma of the skin. Patients with a history of cancer and 5 years or more disease free survival time may be included in the study by agreement with Novartis Medical Expert on a case-by-case basis.
- 7. Patients who develop a COPD exacerbation that required treatment with antibiotics and/or oral corticosteroids and/or hospitalization during screening. Re-screening is permitted after a minimum of 2 weeks after the resolution of the COPD exacerbation (i.e. 2 weeks after the stop of SOC therapy for exacerbation).
- 8. Patients who have had a respiratory tract infection within 4 weeks prior to screening. If a respiratory tract infection occurs during screening, patients can be re-screened after a minimum of 2 weeks after resolution of the respiratory tract infection.
- 9. Patients with history of asthma or any other clinically relevant lung diseases.
- 10. Patients with suspected active pulmonary tuberculosis or currently being treatment for active pulmonary tuberculosis.

Note: Patients with a history of pulmonary tuberculosis can be enrolled if they meet the following requirements: history of appropriate drug treatment followed by negative imaging results within 12 months prior to screening suggesting low probability of recurrent active tuberculosis.

- 11. Patients with pulmonary lobectomy, lung volume reduction surgery, bronchoscopic lung volume reductions, or lung transplantation.
- 12. Patients participating in or planning to participate in the active phase of a supervised pulmonary rehabilitation program during the trial. Participation in a maintenance program is permitted. Note: the supervised pulmonary rehabilitation program as a maintenance program has to be ongoing for at least 3 months at the time of enrollment.
- 13. Patients with a body mass index (BMI) of more than 40 kg/m^2.
- 14. Patients receiving any medications in the classes listed in Table 6-5.
- 15. Patients receiving any COPD related medications in the classes specified in Table 6-6, unless they undergo the required washout period prior to screening and follow the adjustment to treatment program.
- 16. Patients receiving medications in the classes listed in Table 6-2 should be excluded unless the medication has been stabilized for the specified period and the stated conditions have been met.
- 17. Use of other investigational drugs (approved or unapproved) within 30 days or 5 half-lives prior to screening, or until the expected pharmacodynamic effect has returned to baseline (e.g., biologics), whichever is longer; or longer if required by local regulations.
- 18. Pregnant or nursing (lactating) women, where pregnancy was defined as the state of a female after conception and until the termination of gestation, confirmed by a positive human chorionic gonadotropin (hCG) laboratory test.
- 19. Women of child-bearing potential, defined as all women physiologically capable of becoming pregnant, unless they are using acceptable effective methods of contraception during study participation. Acceptable effective contraception methods include:
  - Total abstinence (when this is in line with the preferred and usual lifestyle of the subject). Periodic abstinence (e.g., calendar, ovulation, symptothermal, postovulation methods) and withdrawal are not acceptable methods of contraception.
  - Female sterilization (have had surgical bilateral oophorectomy with or without hysterectomy), total hysterectomy or bilateral tubal ligation at least 6 weeks before taking investigational drug. In case of oophorectomy alone, only when the reproductive status of the woman has been confirmed by follow up hormone level assessment.
  - Male sterilization (at least 6 months prior to screening). For female subjects on the study, the vasectomized male partner should be the sole partner for that subject
  - Barrier methods of contraception: condom or occlusive cap (diaphragm or cervical/vault caps). For the United Kingdom of Great Britain and Northern Island (UK); with spermicidal foam/gel/film/cream/ vaginal suppository.
  - Placement of an intrauterine device (IUD) or intrauterine system (IUS).
  - Note that systemic hormonal contraception (e.g. oral contraception or hormone vaginal ring) is not an acceptable means of contraception due to potential influence of

QBW251 in decreasing the systemic levels of these hormones and therefore making them ineffective (see Section 6.2.1.2)

 If local regulations deviate from the contraception methods listed above to prevent pregnancy, local regulations apply and will be described in the ICF.

Women are considered post-menopausal and not of child bearing potential if they have had 12 months of natural (spontaneous) amenorrhea with an appropriate clinical profile (e.g. age appropriate history of vasomotor symptoms) or have had surgical bilateral oophorectomy (with or without hysterectomy), total hysterectomy or tubal ligation at least 6 weeks ago. In the case of oophorectomy alone, only when the reproductive status of the woman has been confirmed by follow up hormone level assessment is she considered not of child bearing potential.

20. Patients who have not achieved an acceptable spirometry result at screening in accordance with American Thoracic Society (ATS)/ European Respiratory Society (ERS) criteria for acceptability and repeatability (refer to the SOM and vendor manual for Spirometry Guidance).

Note: one re-test may be performed in patients that do not meet the ATS/ERS criteria. Patients who have failed the test and re-test during screening period may be re-screened only once.

### 6 Treatment

### 6.1 Study treatment

The study treatment includes:

- Investigational drug QBW251 dose of 300 mg b.i.d.
- Matching placebo

Details on the requirements for storage and management of study treatment, and instructions to be followed for subject numbering, prescribing/dispensing, and taking study treatment are outlined in the SOM.

Refer to the Section 6.2.4.1 for details of dosing and food intake.

### 6.1.1 Investigational and control drugs

Table 6-1 Investigational and control drugs

Investigational/ Control Drug (Name and Strength)	Pharmaceutical Dosage Form	Route of Administration	Supply type	Sponsor (global or local)
QBW251 300 mg b.i.d	Capsule 	Oral use	Double-blind supply; bottles	Novartis Pharma AG
QBW251 Placebo b.i.d.	Capsule 	Oral use	Double-blind supply; bottles	Novartis Pharma AG

All capsules are of identical appearance to ensure blinding

 QBW251 final pharmaceutical dosage form is a Hard Gelatin Capsule Tab content to maintain double-blind

#### 6.1.2 Additional study treatments

### Background therapy

In order to be eligible for this trial, all subjects will be required to have been on a stable background therapy regimen (LABA/LAMA or LABA/ICS or LABA/LAMA/ICS) and/or macrolides for at least 3 months prior to screening. From screening onwards, subjects will continue with their background therapy until end of study visit.

Background therapy will be taken in the morning approximately between 7 and 10 am for once daily drugs and, in addition to the morning use, approximately 12 hours later in the evening in case of twice daily drugs.

Refer to Table 6-6 regarding background therapy prior to spirometry assessments on visit days.

### Rescue medication

All subjects will be provided with a short-acting beta agonist (salbutamol 100 µg or albuterol 90 µg or equivalent dose). Subjects will be instructed to use it throughout the study on an as needed basis. No other rescue medication is permitted during the study. Rescue medication will be sourced locally. (See Section 6.2.3 for rescue medication further information.)

Sites will be instructed to record the background therapy information and rescue medications in the corresponding eCRF pages.

#### 6.1.3 Treatment arms/group

On Day 1, subjects will be randomized to one of the following 2 treatment arms in a ratio of 1:1

- QBW251 300 mg b.i.d.
- Matching placebo to QBW251 b.i.d.

All subjects will receive their respective QBW251 or placebo capsules for 12 weeks (from Day 1 through Day 84).

#### 6.2 Other treatment(s)

#### 6.2.1 Concomitant therapy

All medications, procedures and significant non-drug therapies administered after the subject was enrolled into the study must be recorded in the concomitant medications/significant non-drug therapies or procedures eCRF page.

Each concomitant drug must be individually assessed against all exclusion criteria/prohibited medication. Please note that the lists provided below may not be exhaustive. If in doubt, the investigator should contact the Novartis Medical Expert before randomizing a subject or allowing a new medication to be started. If the subject is already enrolled, contact Novartis to determine if the subject should continue participation in the study.

### 6.2.1.1 Permitted concomitant therapy requiring caution and/or action

Table 6-2 provides an overview of medications permitted under certain conditions, including bronchodilator medications which need to be withheld for certain timeframes prior to spirometry assessments on visit days, and an overview regarding actions to be taken for antibiotics.

Table 6-2 Medications permitted under certain conditions

Rationale/Group	Medication	Prohibition Period	Action Taken
COPD maintenance background therapy	e.g.Vilanterol, Umeclidinium, Indacaterol Glycopyrronium	Hold treatment for 24 hours (+/-2 hours) prior to each FEV 1 / spirometry measurement on visit days for once daily inhaled background therapy and 12 hours (+/-2 hours) for twice daily inhaled background therapy	In case the washout criterion is not fulfilled, reschedule spirometry accordingly. Trough spirometry (-45 min and -15 min assessments) should be done within 24 hours for once daily inhaled background therapy such as LABA/LAMA or LABA/ICS or LABA/LAMA/ICS from dosing on the previous morning and approximately 12 hours for twice daily LABA/LAMA or LABA/ICS or LABA/LAMA or LABA/ICS or LABA/LAMA/ICS from dosing on the previous evening. Otherwise, postpone visit to the next day where washout criteria can be fulfilled
Rescue medication only	Short-Acting Beta-2 Agonists (SABA)	Hold treatment at least 6 hours prior to each FEV 1 /spirometry measurement	If possible, postpone spirometry measurement on the same day until the washout criterion is fulfilled. Trough spirometry (-45 min and -15 min assessments) should be done within 6 hours after last rescue medication intake
Antibiotics for treatment of exacerbations and macrolides as background medication	Antibiotics, e.g. amoxicillin Macrolides, e.g. erythromycin	Systemic and/or inhaled antibiotics are allowed for treatment of acute infections, or are allowed for the treatment of acute exacerbations.	All data will be set to missing during the exacerbation time(time of SoC intake) and for 14 days thereafter with the exception of macrolides for those

Rationale/Group	Medication	Prohibition Period	Action Taken
		Permanent prophylactic treatment for other indications are not allowed - with the exception of macrolides for COPD subjects with secondary diagnosis of bronchiectasis if those subjects are on stable doses of macrolides at least 3 months before screening and throughout the study.	COPD subjects with a secondary diagnosis of bronchiectasis and on stable dose of macrolides for three months before screening.
		Topical treatment (e.g. use of intraocular, intraconjunctival antibiotic treatments, topical use of creams, etc.) is permitted.	

QBW251 may inhibit the metabolic clearance of co-medications metabolized by CYP1A2. In addition, QBW251 is a time-dependent inhibitor and inducer of CYP3A4/5. Drugs that are sensitive substrates of CYP1A2 have potential for an increase in exposure with QBW251 due to inhibition of CYP1A2. The net effect of QBW251 on CYP3A4 is anticipated to be induction based on results of an oral contraceptive study resulting in a decrease in exposure.

Weak in vitro inhibition of BCRP, OAT1/3, OATP1B1, OATP1B3, UGT1A1 and UGT2B7 was also observed. QBW251 may increase the exposure of drugs which are substrates of the mentioned pathways.

These drugs are listed in Table 6-3 and can be used when indicated and no alternative treatment is available. Safety and efficacy of drug should be monitored accordingly.

The following lists are not considered exhaustive and labels for individual drugs should be referred to.

Table 6-3 Medications which may be co-administered with QBW251 (if no alternative treatment is available)

Page 48

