	
 
Standard clinical laboratory evaluations (hematology, blood chemistry, and urinalysis)
 
	
	Adverse events	

 
To assess QBW251 pharmacokinetics (PK) during and after 12 weeks of treatment.
 
	Assessment of drug exposure (Ctrough collected at pre-dose and Cmax at post-dose) on Day 1, Day 28, Day 56 and Day 84. Cmax and AUC on Day 1 and Day 28 in a subset of the subject population (serial samplings up to 8hr).	

 
To assess the effect of QBW251 compared to placebo after 12 weeks of treatment on spirometry.
 
	
 
Change from baseline in trough FEV1, FVC, and FEV1/FVC.
 
	
Exploratory objective(s)	Endpoint(s) for exploratory objective(s)	

Novartis	Confidential	Page 30
Amended Protocol Version v02 (Clean)		Protocol No. CQBW251B2202

Objective(s) Endpoint(s)

Novartis Confidential Page 31
Amended Protocol Version v02 (Clean) Protocol No. CQBW251B2202

3

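### The rescue row of Protocol Table 6-2 gives two incompatible timings for trough spirometry, so trough FEV1 and FVC may be taken inside the protocol's own rescue washout

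*Protocol*

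**What the plan says.** Protocol section 6.2.1.1 introduces Table 6-2 as covering, among other things, "bronchodilator medications which need to be withheld for certain timeframes prior to spirometry assessments on visit days". The rescue row then makes three statements about timing:

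- Prohibition Period: "Hold treatment at least 6 hours prior to each" FEV1 or spirometry measurement.
- Action Taken, first sentence: "If possible, postpone spirometry measurement on the same day until the washout criterion is fulfilled".
- Action Taken, second sentence: "Trough spirometry (-45 min and -15 min assessments) should be done within 6 hours after last rescue medication intake".

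The measurement concerned is a listed secondary endpoint in Protocol Table 2-1: "Change from baseline in trough FEV1, FVC, and FEV1/FVC". Protocol section 12.5.1 and SAP section 6.3 analyse the spirometry variables with the same repeated-measures model as fibrinogen.

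**The concern.** The row's last sentence places trough spirometry in the period that the hold in the same row excludes, and it contradicts the sentence just before it. Sites read this table as an instruction, so each site has to decide which sentence to follow.

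A site that follows the last sentence measures lung function while a recent dose of a bronchodilator may still be acting. The protocol itself uses salbutamol/albuterol as the test bronchodilator at screening (inclusion criterion 4a, notes). Such a value is not a clean trough.

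Two consequences follow for the change-from-baseline comparison:

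- **Variability.** Time since rescue would vary between subjects, between visits of one subject, and possibly between sites. At the Day 1 assessment, before first dose, any effect should be balanced by randomisation and act only as noise.
- **Bias.** After randomisation, if the arms use rescue to different extents, values raised by recent rescue would be more common in one arm. If QBW251 subjects used less rescue, placebo FEV1 would be raised more and the treatment effect understated. If they used more, it would be overstated.

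**Working it through.** There is no sample-size or power figure to reproduce here. The check is whether the timing rules can be met together.

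**Rescue row.** Let t be hours since the last rescue dose.

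- Rule A (hold, Prohibition Period column): t ≥ 6.
- Rule B (last sentence, Action Taken column): t ≤ 6.
- Both together: [6, ∞) ∩ [0, 6] = {6}. If the upper limit is read strictly (t < 6), no time meets both.

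**Comparison with the once-daily background row of the same table.**

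- Hold: "Hold treatment for 24 hours (+/-2 hours) prior to each FEV"1 or spirometry measurement, so 24 − 2 = 22 to 24 + 2 = 26 hours.
- Trough timing: "should be done within 24 hours for once daily inhaled background therapy", so at most 24 hours.
- Both together: [22, 26] ∩ [0, 24] = [22, 24], a usable two-hour window.

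The same style of wording is therefore workable in the background row, because that hold carries a tolerance. The rescue hold has none, so the conflict is complete apart from a single instant.

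**Fallback.** The background row moves the visit to the following day if its timing cannot be met. The rescue row offers only a same-day delay, and only where feasible. It does not say what to do when that fails.

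**Does anything else in the documents settle it?**

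- Protocol 6.7.1 gives spirometry windows for study drug and daily maintenance medication, but none for rescue.
- Protocol 8.3.1 sends the reader to Table 8-1 for washouts. The legible rows and footnotes of that table give no rescue interval.
- Table 6-6 is redacted, so nothing can be concluded from it.
- The set-to-missing rules in SAP 6.1.3 and 6.2.1 concern fibrinogen and bacterial load around exacerbations and antibiotics. The antibiotic row of Table 6-2 also sets data to missing, but around exacerbation treatment. None of these acts on spirometry by time since SABA.

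**Can the size be computed?** Write p_Q and p_P for the shares of Day 84 trough values taken within the washout in each arm, and r for the mean rise in FEV1 from recent rescue, taken as equal in both arms. Then, approximately:

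bias in the treatment difference = (p_Q − p_P) × r

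The legible text gives none of p_Q, p_P and r. Any figure in mL would be an assumption multiplied by an assumption. Even with p_Q and p_P known, not every early measurement could be put down to this sentence, because the conditional wording of the postponement already permits some.

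**The case against.** The strongest reply is that the row, read whole, tells sites to wait. The introduction to the table, the hold and the first Action Taken sentence all point the same way, and only the last sentence departs from them. On that reading this is loose drafting, and many sites may have observed the hold. This stands in part. It lowers the likelihood that sites were misled, but the last sentence remains an explicit instruction. The postponement is conditional, and there is no next-day fallback.

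A second reply is that rescue use is already a named intercurrent event (Protocol 12.4.1, SAP 6.1.1), with the resulting missing values handled under missing at random (Protocol 12.4.3, SAP 6.1.3.1), and that spirometry uses the same model. That handling is written for fibrinogen. It does not say which spirometry values, if any, are to be treated as missing because of recent rescue.

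Third, sites also receive a separate Spirometry Manual (Protocol 8.3.1), which is not among the documents. It may settle the matter. What sites actually did cannot be judged from here, so variation between sites is possible but not shown.

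Fourth, spirometry is one of many secondary endpoints in a study that Protocol section 12 describes as non-confirmatory. That stands, and it limits the weight of the point.

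A reader might go further and infer that trough FEV1 is biased, on the reasoning that an effective drug must reduce rescue use. The documents do not support this: no legible passage predicts a difference in rescue use between arms, and none gives the data to size one. Nor is a false positive the natural inference. On that same premise, the error would run against QBW251.

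**Conclusion.** The rescue row of Table 6-2 contradicts itself as written and should be reconciled. This is certain from the text: the hold and the last sentence agree only at exactly 6 hours, and no legible passage resolves the conflict.

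The consequence is conditional. If some sites follow the last sentence, trough FEV1, FVC and FEV1/FVC gain variability. If, in addition, rescue use differs by arm, the treatment comparison is biased, in a direction that depends on which arm uses more. The size cannot be computed from the documents. The primary fibrinogen endpoint is not affected. The point deserves correction, but it does not put the trial's main conclusion at risk.

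**What to change.** 1. **Protocol.** The sponsor should reconcile the three statements in the rescue row to one consistent interval, and say what a site does when that interval cannot be met on the day. Which interval applies is the sponsor's decision. The Spirometry Manual should be checked for agreement, as should the washout cross-reference in section 8.3.1.

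2. **Sites.** The reconciled text should go to sites if any visits remain. SAP section 1.4 records a decision to stop the trial before completion, so this step may have little left to act on.

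3. **SAP, before database lock.** Where the time of last rescue can be obtained from visit-day source records, flag spirometry values that do not meet the reconciled interval. Report the trough analysis with and without the flagged values, as a sensitivity analysis. They should stay in the main analysis: rescue use occurs after randomisation and may depend on treatment, so dropping these values could itself introduce bias.

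4. **Data limits.** The eDiary holds puff counts per preceding 12 hours (Protocol 6.2.3), which alone cannot show whether a dose fell within 6 hours of spirometry. If source records do not hold the time either, the report should say that compliance with the interval could not be verified.

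The cost is a protocol clarification, a short SAP paragraph with one additional analysis, and the effort of retrieving times of last rescue from source where they exist.
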